## 11.2.17 Vital Signs Data

This dataset contains information from the Vital Signs (VS) Domain, mapped into a basic data structure.

### 11.2.17.1 *Blood pressure*

For Supine SBP / DBP (mmHg):

**Baseline** is defined as the mean (computed in the eCRF) of the 2 measurements performed on Visit Day 1, at pre-dose (Category equal to 'MEAN'). If missing, it is replaced by the last non missing value recorded prior to the first dose.

**Analysis value** is defined as the value at the visit/ time point (numeric result in standard units). For assessments performed on Visit Day 1, after pre-dose, the analysis value at the time point is retrieved from the record available. For all visits performed after Day 1, the analysis value is retrieved from the record populated with VSCAT = 'MEAN'.

Abnormalities, as defined in table 'treatment emergent notable abnormalities' are populated for each post-baseline assessment individually. In addition, the occurrence of at least one 'Low' and at least one 'High' treatment-emergent abnormality is derived on the subject level for the following time intervals: on Day 1 (from 1 hour post-dose up to discharge), after Day 1 (from discharge on Day 1 through Visit 7 (EOS)) and at any time post-baseline.

For Standing SBP / DBP (mmHg), only the **Analysis value** at the visit is populated.

### 11.2.17.2 *Body weight*

For Body weight (kg), **Baseline**, **Absolute value at each post-baseline analysis visit** and **Absolute change from baseline to each post-baseline analysis visit** variables are populated as described in the general section.

## 11.2.18 Questionnaires Data

This dataset contains information from the Questionnaire (QS) Domain and its supplemental domain, mapped into a basic data structure.

- Modified Systemic Lupus Erythematosus Activity Index-2000 (SLEDAI-2K)

The QS Domain contains the 23 individual descriptors but also the total SLEDAI-2K score and the combined musculoskeletal and mucocutaneous manifestations subscores.

Two additional parameters are created:

The **Mucocutaneous Score** is defined as the weighted sum of each of the individual descriptors for the applicable organ class, i.e. mucosal ulcers, rash, and alopecia. It can be computed by summing up the standardized result for each descriptor.

The **Musculoskeletal Score** is defined as the weighted sum of each of the individual descriptors for the applicable organ class, i.e. arthritis and myositis. It can be computed by summing up the standardized result for each descriptor.

The usual **Baseline, Absolute value at each post-baseline analysis visit, Absolute and percent change from baseline to each post-baseline analysis visit** variables are defined for the total score and for the 3 sub-scores based on the numeric result (standardized).

The **Baseline Category** is defined, for the total score only, as ‘ $\geq 6$ ’ and ‘ $< 6$ ’.

The **Occurrence of an increase from baseline  $> 3$ ,  $> 6$ ,  $> 12$**  are defined, for the total score only, at each visit, based on the absolute change from baseline.

[figure not shown]
- Physician's Global Assessment of disease (PGA)

[figure not shown]
The QS Domain contains the original value recorded on the eCRF (length from 0 to 100 mm) and the standardized value (from 0.00 to 3.00).

The usual **Baseline, Absolute value at each post-baseline analysis visit, Absolute and percent change from baseline to each post-baseline analysis visit** variables are defined based on the numeric result (standardized).

- 36-Item Short Form Health Survey v2 (SF 36v2TM) questionnaire

The QS Domain contains the original value (decode format) recorded on the eCRF (eg., ‘Excellent’, ‘All of the time’) and the standardized value as specified in the SF-36 v2 manual.

The **Analysis value (Character)** is defined for the ‘parent records’ only and contains the Finding in Original Units.

The **Baseline value (Character)** is defined for the ‘parent records’ only and contains the Finding in Original Units.

For all derived parameters (especially raw scores, norm-based scores and the health transition item), **Baseline** and **Change from baseline** are populated as described in the general section.

### 11.2.19 Spirometry Data

The dataset contains the information from the Respiratory System Findings (RE) and its supplemental domain, in a basic data structure, restricted to the ‘best’ records populated by the independent central reader (Sponsor-Defined Identifier equal to ‘0’).

| Test Code | Test Label                              | Test Unit | Parameter (N) | Parameter Code | Parameter                                       |
|-----------|---|-----------|---------------|----------------|---|
| FVC       | Forced Vital Capacity                   | L         | 1             | FVC            | Forced Vital Capacity (FVC) (L)                 |
| FEV1      | Forced Expiratory Volume in 1 Second    | L         | 2             | FEV1           | Forced Expiratory Volume in 1 Second (FEV1) (L) |
| FEV1FVC   | FEV1/FVC                                | RATIO     | 3             | FEV1FVC        | FEV1/FVC  |
| FEV1PRED  | Predicted FEV1                          | L         | 4             | FEV1PRED       | Predicted FEV1 (L)                              |
| FEV1PP    | Percent Predicted FEV1                  | %         | 5             | FEV1PP         | Percent Predicted FEV1 (%)                      |
| FVCPPRED  | Predicted FVC                           | L         | 6             | FVCPPRED       | Predicted FVC (L)                               |
| FVCPP     | Percent Predicted Forced Vital Capacity | %         | 7             | FVCPP          | Percent Predicted FVC (%)                       |
| PEF       | Peak Expiratory Flow                    | L/s       | 8             | PEF            | Peak Expiratory Flow (L/s)                      |
| FEF2575   | Forced Expiratory Flow 25-75%           | L/s       | 9             | FEF2575        | Forced Expiratory Flow 25-75% (FEF) (L/s)       |
| FEF25     | Forced Expiratory Flow 25%              | L/s       | 10            | FEF25          | Forced Expiratory Flow 25% (FEF) (L/s)          |
| FEF50     | Forced Expiratory Flow 50%              | L/s       | 11            | FEF50          | Forced Expiratory Flow 50% (FEF) (L/s)          |
| FEF75     | Forced Expiratory Flow 75%              | L/s       | 12            | FEF75          | Forced Expiratory Flow 75% (FEF) (L/s)          |

In this dataset, the 12 parameters are considered highly dependent, the results of different ‘best’ records cannot be mixed. The definition of **Analysis Record Flag** is slightly modified here, it is valid for a set (date/ time) of ‘best’ values i.e.,

- Prior to first study drug administration

The latest set of 'best' values carrying the highest FVC (L), with the highest quality, is retained for analysis.

If more than one set of 'best' values is done on the same day then an 'Acceptable' test is taken in preference to a 'Borderline' test. If all sets on one day have the same quality (BTR Grade Code equal to 'Acceptable' or 'Borderline') then the highest value is taken. If after this, there are still two sets with either the same value and the same quality then the last set using the time of assessment is used.

- After first study drug administration

The first set of 'best' values carrying the highest FVC (L), with the highest quality, is retained for analysis.

If more than one set of 'best' values is done on the same day then an 'Acceptable' test is taken in preference to a 'Borderline' test. If all sets on one day have the same quality (BTR Grade Code equal to 'Acceptable' or 'Borderline') then the set of 'best' values carrying the lowest FVC (L) is taken.

For each parameter, the **Baseline** Value is extracted from the same set of 'best' values identified thanks to the **Analysis Record Flag** defined above. It can be defined as the highest of the best value(s) populated by the independent central reader (Sponsor-Defined Identifier equal to '0') on valid assessments (BTR Grade Code equal to 'Acceptable' or 'Borderline') performed before first study treatment intake. If more than one set of tests is done on the same day then an 'Acceptable' test is taken in preference to a 'Borderline' test. If all tests on one day have the same quality (BTR Grade Code equal to 'Acceptable' or 'Borderline') then the highest value is taken. If after this, there are still two tests with either the same value and the same quality then the last test using the time of test is used.

For each parameter, the **Analysis value** is extracted from the same set of 'best' values identified thanks to the **Analysis Record Flag** defined above. It can be defined as the best value populated by the independent central reader (Sponsor-Defined Identifier equal to '0') on valid assessments (BTR Grade Code equal to 'Acceptable' or 'Borderline') at each post-baseline visit. If several best values of the same quality are available at the same visit, the highest value is taken in preference to a highest value (i.e., the value leading to the lowest change from baseline).

**Absolute and percent change from baseline to each post-baseline analysis visit** variables are populated as described in the general section (except for Predicted FVC (L) and Predicted FEV1 (L) which hold constant values).

For FVC (L) and FEV1 (L), for each post-baseline assessment, if the percent change from baseline is lower than -15%, the criterion 'Decrease from baseline > 15%' is populated to Y.

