- (5) On Day 1 and at re-initiation, SBP/DBP assessment and 12-lead ECG will be done pre-dose and hourly until 6 h post-dose; after 6 h, subjects may be discharged from the hospital if they meet the discharge criteria, otherwise SBP/DBP assessments and 12-lead ECG will be performed hourly until discharge criteria are met. If discharge criteria are not met after 12 h, the subject must be permanently discontinued. At all other visits, only pre-dose SBP/DBP assessments and 12-lead ECG will be performed.
- (6) At Screening, SBP/DBP will be assessed in supine position and after 1 to 3 minutes in standing position to assess orthostatic hypotension. At all other visits, SBP/DBP will be assessed in supine position.
- (7) At Screening, 24 hour ECG-Holter will start before 12:00. On Day 1, 24 hour ECG-Holter will start immediately before dosing.
- (8) Two spirometry assessments will be performed at Visit 1 (Screening). The assessments should be at least 5 days apart. The last assessment will count as baseline.
- (9) Hematology assessments including coagulation tests will be performed at each visit until EOS
- (10) Serum pregnancy tests will be performed at Screening and EOS. Urine pregnancy tests will be performed at all other visits (including telephone calls FU, 11 weeks and 16 weeks after study treatment discontinuation).
- (11) IgM, IgG, IgA, CRP, fibrinogen, and BLyS will be measured in serum. At Randomization visit only, anti-Smith, anti-cardiolipin, and anti-ribosomal P will also be measured. EDTA plasma samples will be shipped via central laboratory to Actelion for analysis of CXCL10 and other soluble biomarkers potentially related to SLE and/or S1P1 modulation.
- (12) Blood samples will be shipped via central laboratory to Actelion for lymphocyte subsets analysis.
- (13) No study drug dispensing at V3 and re-initiation visit
- (14) All AEs and SAEs that occur after signing the Informed Consent Form and up to 6 weeks (AEs) or 16 weeks (SAEs) after study treatment discontinuation must be reported.
- (15) Prior to randomization, the following central laboratory results must be available to confirm eligibility: ANA, anti-dsDNA, Hepatitis B surface antigen, Hepatitis C, HIV1 and HIV2, varicella-zoster virus, urine protein-to-creatinine ratio, ALT/AST/TBIL, pregnancy test (if applicable).
- (16) EOT visit should preferably take place 1 day after last study treatment dose, and no later than 7 days.

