#### 7.2.6 Spirometry

Spirometry will be performed at all scheduled visits except Visit 2 (Randomization). Spirometry at Visit 1 (Screening) will consist of two assessments performed at least 5 days apart during the Screening period. Spirometry at Visit 3 (Week 2) can be performed up to 3 days prior to or after the visit date. Spirometry from Visit 4 (Week 4) to Visit 7 (EOS) can be performed up to 5 days prior to or after the visit date. All spirometry assessments should preferably be performed in the morning at approximately the same time to avoid diurnal variation, and prior to study drug intake.

Spirometry testing will assess FVC and FEV1.

A central reader will provide equipment and a PFT manual with detailed instructions for the procedures, calibration and validation of spirometers. All recorded spirometry values will be transmitted to the centralized provider, and will be reviewed by independent central readers. Quality of the assessments will be evaluated for compliance with ATS/ERS criteria [Miller 2005a, Miller 2005b], and queries may be sent to the sites for clarification. If quality issues are identified, additional training will be provided. The selection of the highest (largest) FEV1 and FVC values to be used for the main endpoint derivations will be validated by the independent central readers prior to being electronically transferred to the sponsor. No data will be reported in the eCRF.

PFT values that trigger study drug discontinuation will be flagged and sent to the sites and the sponsor. Any clinically relevant PFT abnormality detected after signature of informed consent must be reported as an AE or SAE as appropriate [see Section 10] and

must be followed until the value returns to within the normal range or is stable, or until the change is no longer clinically relevant.

The predicted normal values for FEV1 and FVC used to determine the exclusion and discontinuation criteria [see Section 5.1.10.3] will be those as defined by the European Community for Coal and Steel including ethnic group adjustments [Quanjer 1993].

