### **11 STATISTICAL METHODS**

#### **11.1 General considerations**

All statistical analyses will be conducted by Actelion or by designated CROs supervised by Actelion.

The SAP for final analysis will be approved prior to database lock. The SAP for the interim safety review will be finalized prior to unblinding the study by the independent ISAC. The SAPs provide the full details of all analyses, data displays, and algorithms to be used for data derivations.

All data will be listed, and endpoints will be summarized by appropriate descriptive statistics (tables or figures), typically including:

- number of non-missing observations, number of missing observations, mean, standard deviation, median, Q1 (first quartile), Q3 (third quartile), minimum and maximum for continuous endpoints;
- number of non-missing observations, number of missing observations and frequency with percentage per category (percentages based on the number of non-missing observations) for categorical endpoints;
- number of subjects at risk, cumulative number of events, cumulative number of censored observations and Kaplan-Meier estimates of the survival function for time-to-event endpoints.

Baseline is defined as the last assessment prior to initiation of the study treatment.

Absolute changes from baseline are defined as: post-baseline value minus baseline value, i.e., a positive sign indicates an increase as compared to baseline.

A percentage (relative) change from baseline is defined as the absolute change from baseline divided by the baseline value (if the baseline value does not equal 0) multiplied by 100.

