## 11.2 Analysis variables

### 11.2.1 General

**Baseline value** is defined as the last non-missing value before date and time of first dose intake of double-blind treatment.

**Analysis value** is defined as the value at the visit (numeric result in standard units).

**Absolute change from baseline** is defined as post-baseline value minus baseline value, i.e., a positive sign indicates an increase as compared to baseline.

**Percent change from baseline** is defined as the absolute change from baseline divided by the baseline value (if the baseline value is  $> 0$ ) and then multiplied by 100.

**Ratio to baseline** is defined as the value at the visit divided by the value at baseline (if the baseline value is  $> 0$ ).

**Analysis Date** is defined as the numeric SAS date derived from the Date/Time of assessment. It can be an imputed date [cf. section 12 for more details].

**Analysis Start Date** is defined as the numeric SAS date derived from the Start Date/Time of an event. It can be an imputed date [cf. section 12 for more details].

**Analysis End Date** is defined as the numeric SAS date derived from the End Date/Time of an event. It can be an imputed date [cf. section 12 for more details].

**Analysis End Relative Day** is estimated for several assessments, including AE end, treatment interruptions, concomitant medication end. It refers to the number of days between the end of the specific event and the first study treatment intake.

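### SAP 11.2.19 leaves it unclear whether the spirometry baseline is the last or the highest pre-dose session, and its rule for choosing among repeat post-baseline values is garbled

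*SAP*

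**What the plan says.** **Baseline.** Protocol 7.2.6 sets the pre-dose tests: "Spirometry at Visit 1 (Screening) will consist of two assessments performed at least 5 days apart during the Screening period". Footnote 8 of the visit schedule (Protocol Table 1, repeated in SAP Table 2) says which one counts: "The last assessment will count as baseline". The general definitions agree. Protocol 11.1: "Baseline is defined as the last assessment prior to initiation of the study treatment". SAP 11.2.1: the baseline value "is defined as the last non-missing value before date and time of first dose intake of double-blind treatment".

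SAP 11.2.19 then gives two spirometry-specific statements:
- The record flag for pre-dose data retains "The latest set of 'best' values carrying the highest FVC (L"), with the highest quality. Its tie-breaks apply only to sets done on one day.
- The baseline value is taken from the flagged set, but the next sentence says: "It can be defined as the highest of the best value(s) populated by the independent central reader", across valid tests done before dosing.

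**Post-baseline.** For same-day sets of equal quality, the set "carrying the lowest FVC (L) is taken". The later paragraph on the analysis value, for several values of equal quality at one visit, says "the highest value is taken in preference to a highest value", and explains this in brackets as the value giving the lowest change from baseline.

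**Use.** Change in FEV1 and FVC, and a fall of more than 15% from baseline, are safety endpoints (Protocol 6.2, SAP 5.8.11). SAP 10.9.6 tabulates the falls by visit with Clopper-Pearson intervals. Protocol 5.1.10.3, Table 2, applies a 15% threshold during conduct, relative to the study baseline.

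**The concern.** Section 11.2.19 can be followed faithfully to two different baselines. The two required screening sessions are at least 5 days apart, so the same-day tie-breaks cannot choose between them. What remains is *latest* and *highest* in one phrase with no order, followed by a sentence that says *highest* alone. SAP section 4, which records changes and clarifications to the protocol's analyses, does not mention spirometry.

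If *highest* is programmed, the maximum of two noisy sessions is compared with a single later session. That lowers the average change and adds threshold falls through measurement error alone. The reported events may also fail to match those judged against the study baseline during conduct.

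The post-baseline wording is a smaller matter. It bites only where a visit holds more than one set. That is foreseeable, because a fall of more than 15% calls for a repeat, preferably within a week, and the analysis windows in SAP Table 11 are wide enough to hold both tests.

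**Working it through.** The plan states no event rate or power for this endpoint, so there is no figure of its own to reproduce.

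**Inputs from the documents**
- Two pre-dose sessions (Protocol 7.2.6).
- Five post-baseline visits: Weeks 2, 4, 8, 12 and EOS (all scheduled visits except Visit 2).
- Event: percent change from baseline below -15% (SAP 11.2.19).

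**Assumed:** within-subject CV between sessions, not given in the documents, range 3% to 8%; independent normal errors; simulation of 1,000,000 subjects per cell.

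**Step 1: baseline shift.** The expected maximum of two independent normal values exceeds the mean by SD/√π = 0.564 SD. Baseline therefore rises by 0.564 × 3% = 1.7%, 0.564 × 5% = 2.8%, or 0.564 × 8% = 4.5% of the true level.

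**Step 2: direction.** A test is below 0.85 × the highest session whenever it is below 0.85 × either session. Every event against the last session is therefore also an event against the highest, and the highest rule can only add events.

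**Step 3: one visit, CV 5%, no true change.** Against the last session, the event is post − 0.85 × baseline < 0. The mean is 0.15 and the SD is 0.05 × √(1 + 0.85²) = 0.0656, so z = 2.29 and the probability is 1.1%. The simulation gives 1.1% for the last session and 2.0% for the highest.

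**Step 4: at least one fall of more than 15% over five visits**

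| CV | True change | Last | Highest |
|---|---|---|---|
| 3% | none | 0.03% | 0.07% |
| 5% | none | 4.7% | 8.4% |
| 8% | none | 25.3% | 39.6% |
| 3% | 5% fall | 2.5% | 4.5% |
| 5% | 5% fall | 21.7% | 34.7% |
| 8% | 5% fall | 46.3% | 65.0% |

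For an arm of 12 at CV 5% with no true change, the expected count is 12 × 0.047 = 0.6 versus 12 × 0.084 = 1.0 subjects.

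**Step 5: between arms.** With no true difference, the rate rises equally in all arms. With a true 5% fall in one arm and none in the other (CV 5%), the difference is 21.7 − 4.7 = 17.0 points with the last session and 34.7 − 8.4 = 26.3 points with the highest.

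**Step 6: one subject.** Screening FVC is 3.2 L then 3.0 L, and 2.6 L on treatment. Against the last session, 2.6/3.0 − 1 = −13.3%, no event. Against the highest, 2.6/3.2 − 1 = −18.8%, an event.

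**Step 7: post-baseline choice.** Two sets of equal quality at one visit, CV 5%, true 5% fall, last session as baseline: 1.4% flagged if the higher value is kept, 11.3% if the lower is kept. The two tests are treated as independent and unselected, although a repeat is normally prompted by a low first test.

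**The case against.** The best defence is that the SAP already agrees with footnote 8. Baseline is drawn from the flagged set, and the flag begins with the latest set. SAP 11.1.2 keeps only the latest pre-dose result, and 11.2.19 describes its own flag as a slight modification. Tie-breaks limited to one day make sense if the latest day is chosen first, and the *highest* sentence is then a loose gloss. This reading is available, so a reader who infers that the SAP has deliberately moved to a maximum baseline goes further than the text allows. It does not remove the problem: no priority is stated, and the sentence that defines the value says *highest* of all valid pre-dose values.

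A reader might also infer that the two post-baseline rules are plainly opposite. The bracketed explanation counts against that. Change is signed (SAP 11.2.1), so the lowest change most naturally means the lowest value, which would agree with the same-day rule; the sentence contrasting *highest* with *highest* is probably a typing error. It can still be read the other way, with *lowest change* as the smallest fall. The direct clash is confined to sets of equal quality on one day.

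The consequence is also limited. Spirometry is summarised descriptively, without a test. SAP 10.9 uses all safety data to EOS for over-study abnormality summaries, and 11.2.19 flags each assessment, so record selection matters mainly for the by-visit tables in 10.9.6.

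**Conclusion.** The inconsistency stands. Section 11.2.19 permits a last-session or a highest-session baseline; only the first matches footnote 8 and the general definitions, and no change is declared. If the highest is programmed, reported falls of more than 15% increase in all arms. The size rests on the assumed CV: negligible at 3% (0.03% versus 0.07%), noticeable at 5% (4.7% versus 8.4%) and large at 8% (25.3% versus 39.6%), over five visits with no true change.

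A reader might infer that this biases the comparison with placebo towards a false signal. The documents do not support that: the baseline is fixed before dosing under randomisation, so equal arms stay equal. Absolute incidence is inflated, and a real difference changes in size. Reported events may also not match the study baseline used in conduct.

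The post-baseline sentence is an editorial defect with a limited effect, on visits with more than one set. Both points should be corrected; neither affects the main pharmacodynamic analysis.

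**What to change.** Amend SAP 11.2.19:

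1. **Baseline.** Rewrite both the pre-dose flag phrase and the baseline-value sentence; deleting only the latter would leave the ambiguity in the flag. Baseline is the set from the last valid (Acceptable or Borderline) pre-dose session, as in footnote 8. For sets on the same day only, use quality, then the existing highest-value rule, then time. A highest-of-two baseline may be kept only as a labelled sensitivity analysis.
2. **Post-baseline.** Replace the selection text in both places with one rule: the valid set closest to the target day, as in SAP 11.1.2, and for same-day sets of equal quality the one with the lowest FVC, as 11.2.19 already states. Say that this same-day rule overrides the general same-day rule in 11.1.2, which takes the latest.
3. **Reconciliation.** State how the SAP baseline relates to the study baseline in Protocol 5.1.10.3, Table 2, so that reported falls can be traced to those judged during conduct.

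The cost is SAP wording and the matching dataset specification. No extra data are needed.
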